2.3. Sample Size

The sample size in Stage I is primarily based on clinical considerations, and the number of subjects actually enrolled in each dose group is determined by the number of subjects who show clinically significant toxicity during the observation period for tolerability. During the expansion stage of PK study, 10-12 subjects are required for each group. The sample size in Stage I is 40-60 subjects.

In Stage II, for cohort 1, assuming that the objective response rate (ORR) of the combination therapy is 30% with a two-sided alpha of 0.05, enrollment of 62 subjects will have a 80% power to ensure that the ORR of the combination therapy has a lower 95% CI limit of > 15%. If the dropout rate is 20%, 78 subjects should be enrolled.

For cohorts 2 and 3, assuming that the point estimate of ORR in each cohort is 30% and the width of the 90% confidence interval is 0.3, 38 subjects are required for each cohort when a 20% dropout rate is considered.

For cohort 4, assuming that the point estimate of ORR is 50% and the width of the 90% confidence interval is 0.4, 20 subjects are required to be enrolled.

In Stage II, the four cohorts require to enroll a total of 174 subjects.

3. STATISTICAL HYPOTHESES

No formal statistical hypothesis, no statistical inferences.

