13 STATISTICAL ANALYSIS

13.1 Determination of Sample Size

The sample size in Stage I is primarily based on clinical considerations, and the number of subjects actually enrolled in each dose group is determined by the number of subjects who show clinically significant toxicity during the observation period for tolerability. During the expansion stage of PK study, 10-12 subjects are required for each group. The sample size in Stage I is 40-60 subjects.

In Stage II, for cohort 1, assuming that the ORR of the combination therapy is 30% with a bilateral alpha of 0.05, enrollment of 62 subjects will have a 80% power to ensure that the ORR of the combination therapy has a lower 95% CI limit of > 15%. If the dropout rate is 20%, 78 subjects should be enrolled.

For cohorts 2 and 3, assume that the ORR point estimate of each cohort is 30% and the width of the 90% confidence interval is 0.3, 38 subjects are required for each group when a 20% dropout rate is considered.

For cohort 4, assume that the ORR point estimate is 50% and the width of the 90% confidence interval is 0.4, 20 subjects are required to be enrolled.

In Stage II, the four cohorts require to enroll a total of 174 subjects.

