13.2 Statistical Hypotheses

The primary endpoint in Stage II is ORR.

Null hypothesis: $ORR = 15\%$

Alternative hypothesis: $ORR \neq 15\%$

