5. STATISTICAL ANALYSIS

All efficacy and safety analyses will be based on the following populations/groups:

- **Driver gene negative population:** Subjects who are negative or not tested for EGFR and also negative or not tested for ALK fusion gene are classified into negative population. Including:
 - (1) Apatinib 250 mg + SHR1210 200 mg (Stage I): subjects who are negative or not tested for EGFR and also negative or not tested for ALK fusion gene;
 - (2) Cohort 1;
 - (3) Cohort 3;

Apatinib 250 mg + SHR1210 200 mg are used in both Cohorts 1 and 3 in Stage II.

- **Driver gene positive population:** Subjects who are positive for EGFR or ALK fusion gene are classified into positive population. Including:
 - Subjects who use apatinib 250 mg + SHR1210 200 mg and are positive for EGFR or ALK fusion gene in Stage I;
 - Cohort 2: Apatinib 250 mg + SHR1210 200 mg are used in Cohort 2.
- **Cohort 4:** Apatinib 250 mg + SHR1210 200 mg are used in Cohort 4.
- **Apatinib 375 mg + SHR1210 200 mg:** Only subjects who receive apatinib 375 mg + SHR1210 200 mg in Stage I are included.

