5.3. Efficacy Analysis

The efficacy analysis will be performed based on the investigator's assessments. BOR, ORR, and CBR will be analyzed based on the FAS, PPS, and ES. DOR, TTR, 12-OS%, and OS will be analyzed based on the FAS. See [Table 1](#) for details. Efficacy should be presented by cohort/group.

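### The SAP drops the 15% ORR hypothesis but keeps the Cohort 1 power claim built on it, and names no decision rule, primary population or primary analysis set for that claim

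*SAP*

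**What the plan says.** Protocol 13.2 states that "The primary endpoint in Stage II is ORR" and gives a null of 15% against a two-sided alternative, without saying which cohort it applies to. Protocol 13.1 supplies the link for Cohort 1: "enrollment of 62 subjects will have a 80% power to ensure that the ORR of the combination therapy has a lower 95% CI limit" above 15%. SAP 2.3 repeats this, "assuming that the objective response rate (ORR) of the combination therapy is 30% with a two-sided alpha of 0.05". Cohorts 2, 3 and 4 are sized on the width of a 90% interval, not on power.

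The section that follows, SAP 3, reads in full "No formal statistical hypothesis, no statistical inferences". The SAP introduction says it is based on protocol version 5.0 and gives no reason for the change.

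SAP 5 opens with "All efficacy and safety analyses will be based on the following populations/groups" and lists four: driver gene negative, driver gene positive, Cohort 4, and the 375 mg Stage I group. Cohort 1 appears only as a component of the first, with Cohort 3 and the Stage I 250 mg subjects who are EGFR/ALK negative or untested. SAP 5.3 adds that "BOR, ORR, and CBR will be analyzed based on the FAS, PPS, and ES" and that efficacy is to be presented by cohort or group. SAP 5.3.2 gives ORR a two-sided 95% Clopper-Pearson interval.

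**The concern.** Alpha and power describe a test. A plan that disclaims all inference cannot also carry an 80% power statement; one of the two has to go.

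The pool is not a substitute for Cohort 1. Under Protocol 5.1, Stage I subjects had second-line or later chemotherapy, while Cohort 1 had one platinum doublet; Cohort 3 has a different histology. The only 15% benchmark left in the SAP's analysis text is the forest-plot reference line in SAP 5.3.11, which is drawn for the pooled populations.

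The trial is open-label, SAP 5.3 uses investigator assessments, and the SAP is to be finalised only before database lock. With no population or set named, the choice could be made when responses are already known, and the pool and Cohort 1, or two analysis sets, can give different answers to the 15% question.

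**Working it through.** **Inputs.** Null 15% (Protocol 13.2); assumed ORR 30%, two-sided alpha 0.05, n = 62, dropout 20% (Protocol 13.1, SAP 2.3); Clopper-Pearson interval (Protocol 13.4.3, SAP 5.3.2). The lower limit for x responders in n is L(x, n) = the 2.5% quantile of Beta(x, n − x + 1). Success means L > 15%.

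**1. The plan's own figures reproduce.**
- L(15, 62) = 14.2% and L(16, 62) = 15.5%, so 16 responders are needed.
- Power = P(X ≥ 16 | 62, 0.30) = 80.3%. One-sided error = P(X ≥ 16 | 62, 0.15) = 1.9%.
- 62 / 0.8 = 77.5, rounded up to 78. Stage II total: 78 + 38 + 38 + 20 = 174.

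The sizing is sound, and it matches the exact interval that the SAP prescribes.

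**2. The same rule on the FAS.** L(18, 78) = 14.3% and L(19, 78) = 15.3%, so 19 responders are needed.
- If ORR is 30% in all 78: P(X ≥ 19 | 78, 0.30) = 88.9%. Error at 15%: 2.0%.
- If 20% are dosed but unevaluable and count as non-responders, the FAS ORR is 0.30 × 0.8 = 24%, and P(X ≥ 19 | 78, 0.24) = 51.4%.

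**3. Evaluable set (ES) against FAS, if exactly 62 of 78 treated are evaluable.**

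| Responders | Lower limit, ES (n = 62) | Lower limit, FAS (n = 78) |
|---|---|---|
| 16 | 15.5% | 12.2% |
| 17 | 16.9% | 13.2% |
| 18 | 18.2% | 14.3% |

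All three counts pass in the ES and fail in the FAS. At ORR 30%, P(16 ≤ X ≤ 18 | 62) = 80.3% − 50.4% = 30%. The zone shrinks with more evaluable subjects: 8% at 70, 6% at 74 and 0% at 76.

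**4. Pool against Cohort 1.** The number of driver-negative or untested Stage I subjects at 250 mg is not given. At most 12 + 12 = 24 subjects enter that dose group (tolerability plus PK expansion), so I assume s = 0 to 24. The pool is N = 78 + 38 + s = 116 to 140, of which Cohort 1 is 56-67%. For each N, r is the smallest count with L(r, N) > 15%, and the pass probability is P(A + B ≥ r), with A ~ Bin(78, p₁) and B ~ Bin(38 + s, p₂).

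| Cohort 1 (p₁) | Rest of pool (p₂, assumed) | Pool passes | Cohort 1 alone passes (n = 78) |
|---|---|---|---|
| 15% | 30% | 25-53% | 2% |
| 15% | 20% | 5-11% | 2% |
| 30% | 15% | 67-79% | 89% |

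In the first row the extremes fall at N = 118 (r = 27) and N = 139 (r = 30); the steps come from the discreteness of r.

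For the SAP's non-squamous driver-negative group (Cohort 1 plus Stage I, N = 78 to 102), the 15%/30% scenario gives about 2-16%.

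**The case against.** A reader might infer that the powered question has no answer at all, or that the pool has become the primary analysis. The documents support neither. SAP 2.3 keeps the criterion, SAP 5.3.2 prescribes the very interval that reproduces n = 62, and SAP 5.3 allows results by cohort. A Cohort 1 interval can be produced and read against 15%. That stands. What remains missing is any statement that this row, on a named set, is the primary result; SAP 5 lists only Cohort 4 as a cohort in its own right.

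The SAP also narrows the pool. Sections 5.3.10 and 5.3.11 define a non-squamous driver-negative group and split it by prior lines, and the first-line subgroup should largely isolate Cohort 1. That is a real mitigation, and it is why the range falls to about 2-16% there. But these are exploratory and subgroup analyses, not a primary population.

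It is tempting to quote the largest figures as expected behaviour. They are scenarios. The pool result depends on an assumed 30% elsewhere and an unknown Stage I count. The ES/FAS reversal requires all 16 dropouts to be dosed and never scanned: one post-baseline scan keeps a subject in the ES (any new anti-tumour treatment must not precede it), undosed subjects leave both sets, and dropout is not defined.

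Finally, Protocol 13.4.1 says that results are mainly descriptive. That wording does not cancel a stated null, but a descriptive Stage II would be coherent if it were declared openly.

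**Conclusion.** The contradiction is on the page: SAP 3 conflicts with Protocol 13.2 and with SAP 2.3. The only powered claim in Stage II, covering 78 of 174 subjects, has no decision rule, primary population or primary analysis set. It would be too broad to say that the whole trial is sized on this test, because Cohorts 2 to 4 are sized on precision. The sample-size arithmetic is not in error.

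The possible consequence is material but depends on assumptions. With Cohort 1 at the null and the rest at 30%, the pool clears 15% in 25-53% of trials instead of 2%, and less often if the rest respond less. A reversal between ES and FAS has up to 30% probability at ORR 30%, if only 62 of 78 treated are evaluable. This should be settled before database lock, because a choice made after results are known would not be credible.

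**What to change.** **If the test is intended:**
1. In SAP 3 and Protocol 13.2, state: *Cohort 1 (Stage II only), FAS. H0: ORR = 15%, two-sided alpha 0.05. Success if the lower limit of the two-sided 95% Clopper-Pearson interval exceeds 15% (at least 19 of 78 if 78 are treated). ES and PPS are supportive. Cohorts 2-4 and all pooled groups are estimation only.* Do not add 16 of 62 as an alternative threshold; that is an ES rule and would bring the ambiguity back.
2. In SAP 5, list Cohort 1 and Cohort 3 as analysis groups in their own right, with the pools as supportive.
3. In SAP 2.3 and Protocol 13.1, state that 80% refers to 62 evaluable subjects, and that FAS power for 78 is 89% at a 30% FAS ORR and 51% if 20% are dosed and count as non-responders.

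**If Stage II is meant to be descriptive:** amend Protocol 13.2 and withdraw the alpha and power claim from both documents. Cohort 1 must still be reported separately, on one named primary set.

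The choice is the sponsor's. Either route costs a few sentences in the SAP and the protocol and needs no new data. Under the first, the stated power may look less favourable on the FAS.

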4. STUDY ENDPOINTS

4.1. Efficacy Endpoints

4.1.1. Objective response rate (ORR)

ORR (according to RECIST v1.1) refers to the percentage of subjects with complete response or partial response (CR or PR), and subjects with first assessment as CR/PR should be reexamined 4 weeks later.

The ORR will be assessed based on the documented efficacy evaluation from the date of first dose to the date of disease progression (PD) or the start of new anti-tumor treatment, whichever occurs first. For subjects without PD or initiation of new anti-tumor treatment, ORR results will be assessed based on all efficacy evaluations.

4.1.2. Best overall response (BOR)

The best overall response (BOR) will be calculated based on the documented best assessment from the date of first dose to the date of PD or the start of new anti-tumor treatment, whichever occurs first; or to the date of last efficacy evaluation if no PD occurs and no new anti-tumor treatment is initiated. BOR is classified as: CR, PR, SD, PD, and NE. If the tumor is assessed as

PD at a visit, the date of the PD should be recorded as the date of imaging assessment of the target lesion, the date of imaging assessment of the non-target lesion, or the date of discovery of the new lesion, whichever is earlier.

- Confirmed CR: Response evaluation of CR that has been reconfirmed as CR in a response evaluation 4 weeks later.
- Confirmed PR: Response evaluation of PR that has been reconfirmed as CR/PR in a response evaluation 4 weeks later, with no confirmed CR.
- SD: At least one SD (or better, such as CR, PR), with an interval not less than 6 weeks (i.e. ≥ 42 days) between the imaging date and the date of first dose, with no confirmed CR or PR.
- PD: Disease progression without confirmed CR, confirmed PR, or SD.
- NE: All other conditions.

See Appendix 1 for details.

4.1.3. Clinical benefit response (CBR)

Clinical benefit is defined as the percentage of subjects with a BOR of CR, PR, or SD ≥ 24 weeks according to RECIST v1.1.

4.1.4. Duration of response (DOR)

Duration of response is defined as the time from the first documentation of CR or PR to the date of first documentation of PD or death.

The censoring rules are as follows:

- If there is no radiographic PD or death before the start of any new anti-tumor treatment, censoring will be based on the date of the last effective efficacy evaluation prior to the new anti-tumor treatment.
- If the subject does not have radiographic PD or die before the end of study or dropout, and has not received new anti-tumor treatment before the end of study or dropout, censoring will be based on the date of the last effective efficacy evaluation.
- For death or PD occurring after two or more missed planned visits, censoring will be performed based on the date of the last effective efficacy evaluation prior to death or PD.

4.1.5. Time to response (TTR)

Time to response is defined as the time from the date of first dose to the first documentation of CR or PR (whichever occurs first). Tumor response is based on confirmed response. The date of response is the date of first observation, not the date of confirmation.

4.1.6. Progression-free survival (PFS)

Progression-free survival (PFS): defined as the period of time from the date of first dose to the date of the first documented tumor progression (as per RECIST v1.1, regardless of whether treatment is continued) or death of any cause (whichever occurs first).

Censoring rules:

- If there is no baseline tumor measurement or there is baseline tumor evaluation but with missing tumor evaluation after baseline, censoring will be based on the date of first dose.
- If there is no radiographic PD or death before the start of any new anti-tumor treatment, censoring will be based on the date of the last effective efficacy evaluation prior to the new anti-tumor treatment.
- If the subject does not have radiographic PD or die before the end of study or dropout, and has not received new anti-tumor treatment before the end of study or dropout, censoring will be based on the date of the last effective efficacy evaluation.
- For death or PD occurring after two or more missed planned visits, censoring will be performed based on the date of the last effective efficacy evaluation prior to death or PD.

4.1.7. 12-month overall survival rate (12-OS%)

The 12-month overall survival rate refers to the probability of being alive at Month 12 from the first dose of study treatment, and is assessed by Kaplan-Meier method.

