Criteria for Study Termination	
The termination criteria of this study include but are not limited to the following:
 
 1. Discovery of unexpected, important, or unacceptable risks to the subjects; 2. Major errors in the protocol found during the implementation of the study; 3. Ineffective study drug/treatment, or meaninglessness to continue the study; 4. The sponsor decides to terminate the study due to reasons such as serious delay in the enrollment of subjects or frequent protocol deviations.
Safety Endpoints	
The severity of AEs will be determined according to the CTCAE V4.0.3 criteria. The adverse event record form should be filled out correctly during the study, including the onset time, severity, duration, actions taken, and outcomes of the adverse events.

Efficacy Evaluation	
The enrolled subjects shall undergo 1 imaging evaluation every 2 cycles (8 weeks). After 6 months from the first dose, clinical tumor imaging evaluation will be performed once every 12 weeks \pm 7 days as appropriate. Tumor efficacy will be evaluated based on RECIST 1.1 criteria, and the first evaluation of PR/CR subjects must be confirmed 4 weeks later.

Determination of Sample Size	
The sample size in Stage I is primarily based on clinical considerations, and the number of subjects actually enrolled in each dose group is determined by the number of subjects who show clinically significant toxicity during the observation period for tolerability. During the expansion stage of PK study, 10-12 subjects are required for each group. The sample size in Stage I is 40-60 subjects.
 
Stage II: For cohort 1. Assuming that the ORR of the combination therapy is 30% with a bilateral alpha of 0.05, enrollment of 62 subjects will have a 80% power to ensure that the ORR of the combination therapy has a lower 95% CI limit of $> 15\%$. If the dropout rate is 20%, 78 subjects should be enrolled.
 
For cohorts 2 and 3, assume that the ORR point estimate of each cohort is 30% and the width of the 90% confidence interval is 0.3, 38 subjects are required for each group when a 20% dropout rate is considered.

	
For cohort 4, assume that the ORR point estimate is 50% and the width of the 90% confidence interval is 0.4, 20 subjects are required to be enrolled.
 
In Stage II, the four cohorts require to enroll a total of 174 subjects.

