- [22] Apatinib will be taken orally after meals, once a day, and continued throughout the study (the subjects for the expanded PK study receive the drug starting on Day 22 of Cycle 1. The administration on Day 28 of Cycle 1 and Day 28 of Cycle 2 will be given orally under fasting conditions).
- [23] Return and dispensation of apatinib. Apatinib will be dispensed on Day 1 of Cycle 1 (dispensed to subjects in the drug expansion study from Day 22 of Cycle 1). From Day 1 of Cycle 2, the return and dispensation of apatinib will be performed on Day 1 of each cycle. The remaining drugs will be returned first to verify the dose actually taken before new study drugs are dispensed.
- [24] Imaging examination: Including CT or MRI of the chest, abdomen, and brain. The baseline tumor assessment during the screening period can be extended to up to 3 weeks before treatment. Qualified CT/MRI scan results obtained before signing the informed consent can be used for tumor assessment during the screening period. Bone scan should be performed upon clinically suspected bone metastasis. Absence of cerebral hemorrhage should be confirmed within 21 days before randomization for subjects with stable brain metastases.
- During the treatment period, imaging examinations should be performed under the same conditions as those at baseline (layer thickness of the scan, use of contrast agent, etc.), and the lesions found at baseline should be checked every 2 cycles in the first 6 cycles of the treatment (bone scan shall be performed in the case of suspected bone progression or for CR confirmation). After 6 cycles, imaging examinations can be performed every 3 weeks as appropriate and can be performed upon the discovery of suspected new lesions. Initial assessment of PR/CR must be confirmed after 4 weeks; initial assessment of PD must be confirmed after 4 to 6 weeks (except for significant changes in the subjects' symptoms or rapid tumor progression).
- The window period for imaging examination schedule is ± 7 days. Unscheduled imaging examinations can be performed when progressive disease is suspected (such as worsening of symptoms).

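### The first PFS censoring rule has no exception for death, so it conflicts with the SAP's own PFS definition and can only raise the reported PFS or leave it unchanged

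*SAP*

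**What the plan says.** SAP 4.1.6 runs PFS from first dose to documented progression "or death of any cause (whichever occurs first"). Four censoring rules follow, numbered here in the order in which they appear:

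- **Rule 1** covers subjects with no baseline tumor measurement, and also those for whom "there is baseline tumor evaluation but with missing tumor evaluation after baseline, censoring will be based on the date of first dose".
- **Rule 2** begins "If there is no radiographic PD or death before the start of any new anti-tumor treatment".
- **Rule 3** begins "If the subject does not have radiographic PD or die before the end of study or dropout".
- **Rule 4** begins "For death or PD occurring after two or more missed planned visits" and censors at the last effective efficacy evaluation before the event.

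The protocol synopsis (Efficacy Evaluation) sets the scan interval: "The enrolled subjects shall undergo 1 imaging evaluation every 2 cycles (8 weeks"). Note [24] to the Schedule of Activities adds that "The window period for imaging examination schedule is ± 7 days", and that "Unscheduled imaging examinations can be performed when progressive disease is suspected". SAP Table 1 assigns PFS to the FAS, that is, all dosed subjects. Protocol 13.4.3 names the Kaplan-Meier method but gives no censoring rules.

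**The concern.** Rules 2 and 3 apply only if there has been no radiographic progression and no death. Rule 1 carries no such condition. Take a subject who dies in week 5 without a post-baseline scan and has missed no visit. Under the definition and by the implication of rule 4, this is an event on the date of death. Under the wording of rule 1, it is a censored observation on day 1. The SAP does not say which rule prevails.

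If rule 1 prevails, the subjects with the worst outcome contribute nothing to the PFS curve. That is informative censoring in one direction. There is no concurrent control arm in which a similar error could offset it, so readers can set these PFS figures only against outside results. The choice would also fall to whoever programs the endpoint, possibly after the deaths are known.

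**Working it through.** The plan states no PFS median, event count or PFS sample size, so there is no planned PFS figure to reproduce. The check covers direction first, then size under stated assumptions.

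**Inputs**

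- First scheduled scan: week 8 ± 7 days, so weeks 7 to 9. The second is at week 16 ± 7 days, so by week 17 at the latest (119 / 30.4375 = 3.9 months).
- Planned enrolment: 78, 38, 38 and 20 in Cohorts 1 to 4 (SAP 2.3).
- Illustrative median m = 4.7 months, from the phase II study of apatinib alone in non-squamous NSCLC (Protocol 1.7.2.4). Its use for the combination is an assumption.
- Share q of subjects who die with no post-baseline scan: not in the documents. The range 2% to 10% is an assumption.

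**Direction.** Let N subjects include k = qN unscanned deaths. At any time t after the last of these deaths, and with no other earlier censoring:

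- deaths counted as events: S(t) = (others event-free at t) / N
- rule 1 applied literally: S(t) = (others event-free at t) / (N − k)

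The second is the first multiplied by 1/(1 − q). With q = 0 they agree; otherwise rule 1 gives the larger value. A death that comes before two scheduled scans have been missed falls by about 3.9 months. The result therefore holds for the 6-, 9- and 12-month rates, and for any median later than that.

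Example: if 8 of 78 subjects (10.3%) died unscanned, 70 would remain at risk after day 1 and none of the 8 deaths would count.

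**Size.** If the remaining subjects have exponential PFS with median m, rule 1 reports m. With the deaths counted, the median solves (1 − q) × 2^(−t/m) = 0.5, so t = m × [1 + log2(1 − q)]. The six-month rate under rule 1 is 2^(−6/4.7) = 41.3%; with the deaths counted it is 41.3% × (1 − q).

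| q | Median, rule 1 | Median, deaths counted | Overstatement | 6-month PFS, rule 1 | 6-month PFS, deaths counted | Factor 1/(1 − q) |
|---|---|---|---|---|---|---|
| 2% | 4.7 | 4.56 | 0.14 months (3%) | 41.3% | 40.5% | 1.02 |
| 5% | 4.7 | 4.35 | 0.35 months (8%) | 41.3% | 39.2% | 1.05 |
| 10% | 4.7 | 3.99 | 0.71 months (18%) | 41.3% | 37.1% | 1.11 |

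**Check on the real scan grid.** A Kaplan-Meier simulation placed scans at weeks 8, 16 and 24 and then every 12 weeks, with the ± 7-day window. At N = 78 the mean overstatement of the median was 0.47 months at q = 5% and 0.90 months at q = 10%. At N = 20 and q = 5%, the rule 1 median was higher in 65% of simulated trials and the same in the rest. It was not lower in any simulated trial.

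**The case against.** The strongest defence is that rule 1 was meant only for subjects without an event. The definition counts every death, and rule 4 is the only rule that expressly censors one, so a careful programmer could read rule 1 that way. This stands as a possible reading. It is not a safe one, because rules 2 and 3 state the condition that rule 1 omits, and nothing sets precedence.

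The defence also limits the scope, and rightly. A reader might infer that every patient who dies before week 8 is dropped and that median PFS is inflated in every cohort. The documents do not support that:

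- Rule 1 reaches only subjects with no post-baseline tumor evaluation at all. An unscheduled scan, or the end-of-treatment scan in Protocol 7.3, takes a subject outside it. Conversely, a death after week 8 with the first scan missed is caught.
- A cohort with no unscanned death has no bias, and in a small cohort with scan-grid event times the median may not move.
- ECOG 0–1 and a life expectancy of at least 12 weeks at entry (Protocol 5.1) should keep q low.

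A small q is not a certain q. The phase I apatinib table in Protocol 1.7.2.2 lists 4 of 68 subjects (5.9%) as dying without evaluation. These were gastric and colorectal cases, with none among the 5 lung subjects, so the figure shows only that such deaths occur.

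Nor is the primary result at risk. PFS is secondary (Protocol 2.2), and SAP Section 3 plans no inference. Unscanned subjects stay in the FAS denominator for ORR, and OS still counts their deaths.

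**Conclusion.** The point holds as an internal conflict in SAP 4.1.6. Rule 1, read literally, contradicts the PFS definition and what rule 4 implies. If it is followed, the KM median and the landmark PFS rates are biased upward or not at all. The direction follows from the rule itself, for time points after the deaths concerned. The size does not: it rests on an assumed q, an assumed exponential shape and a 4.7-month median borrowed from monotherapy. On those assumptions the overstatement is about 0.1 to 0.7 months for q between 2% and 10%, with rates inflated by 1/(1 − q). Censoring living subjects without a post-baseline scan at first dose is not in dispute. Severity: should be fixed before database lock; it is not critical, because the endpoint is secondary and descriptive.

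**What to change.** Reword rule 1 along these lines:

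> If there is no baseline tumor measurement or no post-baseline tumor evaluation, and the subject did not die before missing two consecutive scheduled tumor assessments, censor at the date of first dose; a death before that point is a PFS event on the date of death.

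Two companion changes are needed:

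- In rule 4, replace planned visits with consecutive scheduled tumor assessments. Treatment visits fall every two weeks, so on the present wording a death at week 6 after two missed treatment visits could still be censored. The same phrase in the DoR rules (SAP 4.1.4) should be aligned.
- State that rule 1 does not override a death that qualifies as an event.

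The cost is a few sentences in the SAP and no new data. The reported median PFS may be slightly shorter.
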